# 6.2. Exclusion Criteria

Subjects will be excluded if any of the following exclusion criteria are met:

- 1. Has a history of any severe anaphylactic reaction to blood or any blood-derived product.
- 2. Has selective IgA deficiency or has a history of antibodies to IgA.
- 3. Has clinically significant impairment of cellular or innate immunity at the discretion of the Investigator.
- 4. Has evidence of an active infection at the time of enrolment (i.e. on day of first infusion). Subjects who are asymptomatic but have not completed their course of antibiotics are eligible.
- 5. Has previously completed or withdrawn from this study.
- 6. Is currently receiving, or has received, any investigational agent within the prior three months unless it is an investigational stage III, IIIb IGIV or SCIG.
- 7. Is pregnant (confirmed by a positive result on an HCG-based pregnancy test) or is nursing.
- 8. Is positive for any of the following at screening:

Page 19 of 87

- Serological test for HIV 1&2, HCV, or HBsAg
- 9. Has levels at screening greater than 2.5 times the upper limit of normal as defined at the central laboratory of any of the following:
  - Alanine transaminase (ALT)
  - Aspartate transaminase (AST)
- 10. Has severe renal impairment (defined as serum creatinine greater than two times the upper limit of normal or BUN greater than two times the upper limit of normal for the range of the laboratory doing the analysis); the subject is on dialysis or has a history of acute renal failure.
- 11. Is known to abuse alcohol, opiates, psychotropic agents, or other chemicals or drugs, or has done so within the past 12 months.
- 12. Has a history of DVT, or thrombotic complications of immunoglobulin therapy, or a diagnosis of thrombophilia.
- 13. Suffers from any acute or chronic medical condition (e.g. renal disease or predisposing conditions for renal disease, coronary artery disease, or protein losing state, proteinuria) that the Investigator feels may interfere with the conduct of the study.
- 14. Has an acquired medical condition, such as chronic lymphocytic leukemia, lymphoma, multiple myeloma, chronic or recurrent neutropenia (ANC  $< 1 \times 10^9$ /L).
- 15. Is receiving the following medication:
  - Steroids (long-term daily, ≥ 0.15 mg of prednisone equivalent/kg/day). Requirement for short or intermittent courses of > 0.15mg/kg/day would not exclude a subject.
  - Immunosuppressive drugs
  - Immunomodulatory drugs

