# 7.4.1. Effects on Hepatic, Renal, and Hematologic Function

If the results of any blood test demonstrate a rise to 2.5 times the upper limit of normal in AST, ALT, or bilirubin, these laboratory results will be documented as an AE.

A blood test demonstrating a change in renal or hematologic function will be documented as an AE if considered clinically significant by the Investigator.

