6.2 Safety Endpoints

Safety endpoints include assessment of adverse events and adverse drug reactions, significant changes in vital signs, safety laboratory parameters (including kidney and liver function and Direct Coombs' test), virology, physical examination or medical history during the study.

The variables used to assess safety will be the following:

- Adverse Events
 - The number and percent of adverse events (AEs) including infusion site reactions.
 - The number and percent of infusions associated with one or more AEs that begin during the infusion, up to one hour, 24 hours, 48 hours or within 72 hours after completion of the infusion.
 - Adverse reactions, defined as any AE occurring during the infusions or within 72 hours of the infusion completion OR any AE classed as product related.
 - Thrombotic events
 - Nature, severity, and frequency of AEs (tolerability)
 - Suspected unexpected serious adverse reactions (SUSARs), if any
- Vital signs
- Clinical laboratory tests including tests for hemolysis
- Transmission of viruses
- Physical examination

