10. GENERAL ISSUES FOR STATISTICAL ANALYSES

Subject listings of all data represented in the electronic CRF (eCRF) will be provided. Measurements from subjects excluded from the predefined analysis populations or extra measurements (such as unscheduled or repeat assessments) will not be included in summary tables unless specified otherwise, but will be included in the subject listings. In general, the subject listings will be sorted by subject number and assessment date (and time) if applicable.

Unless otherwise specified, descriptive statistics will include the number of subjects with data to be summarized (n), mean, standard deviation (SD), median, minimum and maximum. The same number of decimal places as in the raw data will be presented when reporting minimum and maximum, 1 more decimal place than in the raw data will be presented when reporting mean and median, and 2 more decimal places than in the raw data will be presented when reporting SD.

All categorical/qualitative data will be presented using absolute counts and percentages. The total number of subjects in the treatment group overall (N) will be used as the denominator for percentage calculations, unless stated otherwise in the table shell. All percentages will be presented as one-decimal point, unless otherwise specified. Percentages equal to 100 will be presented as 100% and percentages will not be presented for zero frequencies.

All analyses and summaries will be produced using SAS® version 9.2 (or higher).

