13.3 Vital Signs

Vital signs tables will show summaries for all ages combined, all pediatrics (2 to 15 years of age) and adults (16 years and over).

Descriptive statistics for vital signs (absolute values and change from baseline) will be presented for each study visit. Descriptive statistics for percent change from pre-infusion value will be presented at each of the post-infusion measurements for the following vital signs: blood pressure (diastolic and systolic), pulse rate, respiration rate and temperature. Since each subject has multiple infusions throughout the study,

the average change over all infusions for each subject will first be calculated, so that the descriptive statistics will summarize the mean change over all infusions for each subject. The pre-infusion value at each infusion will be the average of the measurements recorded at 10 minutes prior to infusion, and at infusion start.

13.4 Clinical Laboratory Evaluations, Tests for Markers of Hemolysis and Viral Transmission Tests

All summaries of laboratory data will be based on the Intent-to-Treat population. Tables will be subset for all pediatrics (2 to 15 years of age) and adults (16 years and over). Tables will also show summaries for all ages combined.

Descriptive statistics and change from baseline values will be provided for biochemistry and hematology results at each visit. The baseline value for each parameter is defined as the last result prior to the first infusion (usually collected on Day 1).

Summaries of urinalysis will be split by type of result: continuous or categorical. For categorical results (e.g., dipstick tests), the table will display the number and percent of subjects with the given result at the specified visit. Continuous results will be summarized as described above for biochemistry and hematology.

Results of tests for markers of hemolysis (Direct Coombs' test, haptoglobin, plasma free haemoglobin and urine hemoseridin) will be summarized by the number and percent of subjects with the given result at each visit. Percentages will be based on the number of subjects in the ITT population for the given infusion schedule. Two additional listings will be produced:

- 1) showing all the above values, and those for serum bilirubin and LDH, for visits in which at least one of the parameters is indicative of hemolysis.
- 2) showing absolute haemoglobin, change from baseline, and Direct Coombs' tests at each visit

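### Significant laboratory change is a safety endpoint, but SAP 13.4 plans no laboratory-based count or shift table for biochemistry and hematology, so affected subjects are counted only indirectly through AE reporting

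*SAP*

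**What the plan says.** **Endpoint.** SAP 6.2, following Protocol 10.1, lists among the safety endpoints "significant changes in vital signs, safety laboratory parameters (including kidney and liver function" and the Direct Coombs' test). Neither section says when a change counts as significant.

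**Planned tables.** For biochemistry and hematology, SAP 13.4 states: "Descriptive statistics and change from baseline values will be provided for biochemistry and hematology results at each visit". SAP 10 fixes the content: "descriptive statistics will include the number of subjects with data to be summarized (n), mean, standard deviation (SD), median, minimum and maximum". It also promises listings: "Subject listings of all data represented in the electronic CRF (eCRF) will be provided". It then restricts what enters the tables: "extra measurements (such as unscheduled or repeat assessments) will not be included in summary tables unless specified otherwise".

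**Other safety data.** SAP 13.4 gives number and percent of subjects by result for categorical urinalysis, hemolysis markers and viral tests. It adds a shift table for the viral tests, and SAP 13.5 has one for physical examination. Two listings cover the hemolysis values and hemoglobin by subject.

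**AE route.** Protocol 7.4.1 makes "a rise to 2.5 times the upper limit of normal in AST, ALT, or bilirubin" an AE. A change in renal or hematologic function "will be documented as an AE if considered clinically significant by the Investigator". SAP 13.2 counts subjects with TEAEs by system organ class and preferred term.

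**The concern.** The endpoint is about subjects with a significant change. The planned biochemistry and hematology tables describe the distribution at each visit. They can show that a large value occurred, but not how many subjects had one, whether the same subject recurs across visits, or whether rises in different analytes coincide. In a trial of 30 to 50 subjects a liver or kidney signal may well be one or two people, so the count is the figure a reader needs. As planned, it would come from AE records, which depend on site recording, on term selection and, for kidney and blood, on investigator judgement. It would not come directly from the central laboratory results.

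**Working it through.** The plan states no figure on this point, so there is none to reproduce. The check sets the planned outputs against the endpoint and adds one illustration.

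**1. What each planned output can answer**

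| Output | Shows a large rise? | Counts subjects from laboratory data? |
|---|---|---|
| By-visit mean, median | Hardly, for one or two subjects | No |
| By-visit minimum, maximum | Yes, at a scheduled visit | No |
| Subject listings (SAP 10) | Yes, unscheduled values included | No |
| TEAE tables (SAP 13.2) | If recorded as an AE | No; counts AE terms |

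**2. Illustration at the protocol's liver limit**

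Inputs: 2.5 x ULN from Protocol 7.4.1; n = 30 (planned evaluable) and n = 50 (maximum enrolled). Assumptions: baseline b = 0.5 or 1.0 x ULN, and all other subjects unchanged.

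Mean change = k x (2.5 - b) / n, in ULN units, when k subjects rise to the limit.

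| n | k | b = 0.5 | b = 1.0 | Subjects affected |
|---|---|---|---|---|
| 30 | 1 | 2.0/30 = 0.067 | 1.5/30 = 0.050 | 3.3% |
| 30 | 2 | 4.0/30 = 0.133 | 3.0/30 = 0.100 | 6.7% |
| 50 | 1 | 2.0/50 = 0.040 | 1.5/50 = 0.030 | 2.0% |
| 50 | 2 | 4.0/50 = 0.080 | 3.0/50 = 0.060 | 4.0% |

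The median change is 0 in every row. With b = 0.5 the maximum change is +2.0 x ULN whether one subject or two rise, so the maximum reveals the event but not the number. For one subject the SD of change is 2.0/sqrt(n): 0.37 at n = 30 and 0.28 at n = 50. A threshold table would report 1/30 = 3.3% (exact 95% CI 0.1% to 17.2%) or 1/50 = 2.0% (0.1% to 10.6%).

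**3. Values outside scheduled visits**

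Protocol Table 2 places hematology and biochemistry after the first infusion at Weeks 2, 5, 9, 17 and 27. A peak found at an unscheduled or repeat test between those weeks is listed, but under SAP 10 it enters no summary table, so the by-visit maximum misses it too.

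**4. How direct the AE count is**

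- Liver: Protocol 7.4.1 requires an AE at 2.5 x ULN. Protocol 10.2 asks for the diagnosis as the AE, so crossings may be spread over several preferred terms. Appendix I, section 1.1, ties laboratory AEs to the investigator's view of clinical significance, which does not match the automatic rule in 7.4.1.
- Kidney and blood: Protocol 7.4.1 gives no number and relies on investigator judgement.
- Hemolysis: Protocol 7.4.2 gives a laboratory criterion, namely a hemoglobin drop of at least 2 g/dL with haptoglobin below the lower limit of normal and a rise in LDH. Its components are tabulated or listed, but no table counts subjects meeting all three.

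**The case against.** The case for leaving SAP 13.4 alone has real substance.

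- **The tables are not means only.** A reader might infer that individual rises are averaged away. The documents do not support that: SD, minimum, maximum and full listings are planned, and a large rise at a scheduled visit appears as the maximum.
- **The liver limit does reach a count.** A reader might infer that nothing counts subjects who cross the protocol's limit. That is too strong: crossings of 2.5 x ULN must be recorded as AEs, and those that are treatment-emergent enter the TEAE tables. What remains is that this count is indirect.
- **The protocol asks only for descriptive summaries** (Protocol 13.4.2), and shift tables suit categorical data most naturally. So there is no breach of the protocol. But subject counts and shift tables are themselves descriptive, and grading against a reference range makes a continuous analyte categorical.
- **There is no numeric on-study kidney limit.** It is tempting to read "serum creatinine greater than two times the upper limit of normal or BUN greater than two times the upper limit of normal" as one. It is an exclusion criterion (Protocol 6.2), as are hemoglobin below 10 g/dL and the ANC figure.
- **Pediatric pooling.** A reader might object that pooled pediatric means lack an age-appropriate reference. The documents say nothing about age-dependent ranges, so that argument is not made here.
- **Table burden.** Protocol 7.4 names 11 biochemistry and 10 hematology measures. Shift tables for all 21 in each pediatric age group, with a minimum of four subjects per group, would be long and nearly empty. This stands and limits the fix.

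**Conclusion.** The concern holds as a gap in safety reporting. The endpoint of significant laboratory change is left undefined, and no laboratory-based threshold or shift table is planned for biochemistry and hematology. Unscheduled and repeat values stay out of the summaries, which widens the gap. Liver crossings are counted only through AE recording and coding; renal and hematologic changes only on investigator judgement.

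In the illustration, one subject reaching the liver limit moves the mean change by 0.03 to 0.07 x ULN and leaves the median at 0, while the informative figure is 2.0% to 3.3% of subjects. Those values rest on the assumed baselines, on no change in other subjects, and on 30 to 50 subjects with data. The finding about the planned tables does not depend on them.

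The documents do not support saying that rises would go unseen or that no count exists at all. The weight is modest: the primary PK analysis, the sample size and the 40% infusion-AE criterion are unaffected.

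**What to change.** Define significant change for this endpoint, and add to SAP 13.4:

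1. Number and percent of subjects meeting the protocol's existing on-study criteria at any post-baseline time, with unscheduled and repeat values explicitly included as an exception to SAP 10:
   - AST, ALT or bilirubin at or above 2.5 x ULN (Protocol 7.4.1);
   - a hemoglobin drop of 2 g/dL or more with haptoglobin below the lower limit of normal and a rise in LDH (Protocol 7.4.2). State how the components are matched in time. In Table 2 haptoglobin falls at Weeks 1, 2, 13 and 27, so scheduled values of all three coincide after the first infusion only at Weeks 2 and 27.
2. Shift tables (low, normal, high on the central laboratory's reference range) from baseline to the worst post-baseline value for the liver, kidney and main hematology analytes, shown for all subjects, adults and pediatrics.

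If the entry limits for creatinine, BUN, hemoglobin or ANC are also used, label them as descriptive reporting cut-points, not on-study limits. Keep the by-visit statistics as support. Protocol 7.4.1 and Appendix I, section 1.1, should also be reconciled on when a laboratory value becomes an AE.

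The cost is some SAP wording and a few extra tables from data already collected, with no new sample or visit. SAP 2.1 still cites Protocol Version 5.0 while the current protocol is Version 6, so an SAP update is due in any case.

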13.5 Physical Examination

Physical examination tables will be subset for all pediatrics (2 to 15 years of age) and adults (16 years and over). Tables will also show summaries for all ages combined.

The number and percent of subjects with assessments of normal, abnormal or not done at screening will be displayed in a summary table for each body system. At each post screening assessment the number and percent of subjects with assessments of no change, normal, abnormal or not done will also be displayed in a summary table for each body system. Percents will be calculated out of the number of subjects with results at a given visit (including assessments indicated as not done).

The end of study assessment will be tabulated against the screening assessment for each body system in a shift table. Percentages will be calculated from the number of subjects with the given result at Screening.

Summary of physical examination results will be based on the Intent-to-Treat population.

13.6 Thromboembolic Events

Monitoring for thromboembolic events (TEEs) will be performed at screening (baseline) and at the Week 27 follow up visit (as well as when clinically indicated); TEEs will be listed.

14. PHARMACOKINETIC ANALYSES

PK analyses are not included in this SAP but documented separately in a PK Analysis Plan. Only the following listings and tables are included in this SAP:

 Listing of IgG levels (trough levels, serial IgG levels at the PK assessment), IgG subclasses, IgA, IgM and antibodies by subject. Trough levels of total IgG, IgG subclasses and IgG antibodies to specific antigens will be summarized descriptively for all the subjects in the ITT group. Tables will be presented for the pediatric subgroups in addition to all subjects, all adults and all pediatric subjects. Trough levels will be compared with those collected at the Screening visit.

15. DEVIATIONS FROM THE PROTOCOL SPECIFIED ANALYSIS

There are no deviations from the protocol specified analysis.

